### 1.1.1 OVERVIEW OF STUDY DISEASE(S)

Incidence and cost to society: An estimated 1 in 5 Americans will develop skin cancer in their lifetime including melanoma, the deadliest form. Melanoma incidence rates have increased three times over the past three decades with two hundred thousand new cases reported in 2020. This number is expected to increase in 2023. When skin cancers are detected at an early stage, survival rates are 98% — compared to late detection of melanoma with metastasis, survival falls to 24% and becomes increasingly fatal.

Skin cancer in the United States: Skin cancer is a problem in the United States with an incidence that has increased significantly in the last three decades. The Oregon Health and Science University Department of Dermatology and Knight Cancer Institute have initiated a War on Melanoma to combat it through early detection (IRB#10561). One crucial component of the War on Melanoma's early detection program is development and implementation of imaging technologies to enable earlier detection of melanomas before they become life-threatening. Previous attempts to provide access to patients through virtual triage from home have relied on triage of PSLCs based upon patient selection – which is attune to subjective observation, bias and limitations. The current standard of care to evaluate a skin lesion of interest in-office (dermatology) is using a dermatoscope.

### 1.1.2 OVERVIEW STUDY INTERVENTION(S)

All Participants of this single-arm prospective trial will be given up to 14 days to **review** the Sklip System instructions, **perform** a self-skin-exam (SSE) at-home, and **identify** pigmented skin lesions of concern (PSLCs). Then, Participants will be instructed to carefully follow provided instructions and **complete** a series of tasks described in Section 3.1 below.

## 1.2 STUDY RATIONALE

### Limitations that we can overcome for layperson at-home self-selection of PSLCs:

- a) **Layperson self-selection triage bias** using subjective selection criteria resulting in low sensitivity & specificity
- b) **Lack of image quality verification prior to doctor consultation** which results in patients submitting low technical quality images (blurry) to DPs in a virtual communication, that are often difficult to evaluate
- c) **DP low confidence when using SCI (non-medical-device assisted) to triage PSLCs in a virtual setting**
- d) **Overuse of DP resources for benign self-selected PSLs and packing the healthcare system with visits** for PSLCs that are concerning for laypersons but often verified to be benign by a DP in-office using dermoscopy
- e) **Reduced access and delay of care** due to increased wait times to see DPs in-office.

#### **Current standard of care for layperson at-home self-selection of PSLCs:**

In the current at-home SSE model, the layperson must first identify a specific PSL based on subjective observation. Then, the identified PSL must raise adequate concern to prompt communication with a DP through scheduling a virtual visit or requesting an in-person spot check. Currently, there is no objective prescreening method for PSLC selection or virtual visit image technical quality submission. If the layperson chooses to call and schedule an in-person visit for a new spot check appointment, the average national wait time to be seen in-person by a MD/DO dermatologist is 3 to 6 months, sometimes more. Alternatively, the layperson may choose to communicate with a DP, typically a MD/DO dermatologist, via virtual communication and send store-and-forwards SCI of their PSLC. Prior to submission, the PSLC SCI (non-medical-device assisted) image quality is not verified and often laypersons send images that are blurry, contain artifacts, or do not make it clear which PSLC is the one of concern amongst an image that contains several skin lesions (moles) in the field of view. This makes confident triage difficult for any DP in a virtual setting and often requires the DP or their team to contact the patient in order to request retaking the SCI again with better technical quality (clear image). Once an appropriate technical quality PSLC SCI is received, the DP uses non-medical-device assisted clinical judgement to make their triage decision into one of three categories:

1. **UNREMARKABLE** (no immediate concern with low clinical suspicion for malignancy, suggest the patient to self-monitor until the PSLC becomes unstable)
2. **SUSPICION** (concern with moderate to high suspicion for malignancy, recommendation to convert to an in-person visit to evaluate the PSLC with a dermatoscope, biopsy is possible)
3. **ERROR** (ask patient to retake a clear SCI image, if unsuccessful on the second attempt, convert to an in-person visit to evaluate with a dermatoscope, biopsy is possible).

#### **Current evaluation of PSLCs by the Sklip System:**

The Sklip System may safely improve triage of layperson self-selected PSLCs in an at-home environment by transitioning a regulated triage tool (FDA Class 2) into the hands of laypersons.

After a PSLC is initially identified by the layperson, the SMSA (Sklip Ai), an artificial intelligence tool, uses objective modified dermoscopy Three-Point Checklist (MD3PC): (asymmetry (including atypical network), round structures and blue-white color) to triage PSLs into one of three categories:

1. **UNREMARKABLE** (no immediate concern, limited or no positive MD3PC, with low concern for malignancy or pre-malignancy, the SMSA output provides information and suggests the layperson to self-monitor the PSLC every three months, if the user does not understand the initial SMSA output result (Sklip Mole Scan Result) or the PSLC ever becomes unstable (changes), product labelling clearly instructs the user to contact a healthcare Provider for an in-person visit, biopsy is possible)
2. **SUSPICIOUS** (positive MD3PC with moderate to high concern for malignancy, the SMSA output result provides information and strongly suggests the layperson to contact a healthcare Provider for an in-person visit, biopsy is very possible)
3. **ERROR** (uploaded image does not meet SMSA criteria and an assessment of DDI cannot be made, the SMSA output result provides information how to properly retake DDI, if the user is unsuccessful after three (3) attempts, clear product labelling instructs the layperson to contact a healthcare Provider for an in-person visit, biopsy is possible)

### **How the Sklip System Improves Triage:**

The Sklip System has the potential to improve triage of PSLCs and address the current limitations:

a) **Layperson self-selection triage bias** using subjective selection criteria resulting in low sensitivity & specificity.

Potential solution: Sklip System uses objective dermoscopy criteria (MD3PC) to evaluate a self-selected PSLC which may result in safe accuracy based on pre-specified performance goals by the FDA.

b) **Lack of image quality verification prior to doctor consultation** which results in patients submitting low technical quality images (blurry) to DPs in a virtual communication, that are often difficult to evaluate.

Potential solution: The Sklip dermatoscope is a medical grade device that enables the layperson user to take a medical grade in-office like quality image from home by controlling the light source, magnification and fixed placement of the device flat against the skin. The SMSA first verifies whether a digital dermoscopy image (DDI) is technically appropriate for evaluation, which may reduce the number of blurry DDI sent to a dermatology provider in a virtual communication. After the SMSA verifies technical quality of the DDI, the second step is the evaluation of the DDI based on trained MD3PC as described above.

c) **DP low confidence when using SCI (non-medical-device assisted) to triage PSLCs in a virtual setting.**

Potential solution: The Sklip System enables a layperson to take a medical grade DDI. It is well established in literature that the use of DDI improves both accuracy and confidence of PSLC triage. Additionally, the Sklip System will automatically categorize the PSL into: SUSPICIOUS, UNREMARKABLE, or ERROR, prior to the layperson contact with their dermatologist, which may result in safe accuracy based on pre-specified performance goals by the FDA.

d) **Overuse of DP resources for benign self-selected PSLs and packing the healthcare system with visits** for PSLCs that are concerning for laypersons but often verified to be benign by a DP in-office using dermoscopy.

Potential solution: Sklip System may help reduce layperson concerns about benign skin lesions due to safe and accurate triage based on pre-specified performance goals by the FDA. This may allow DPs to have more confidence not seeing the patient in person for an otherwise benign concern and improve access for patients with actual malignancies that may be detected by the SMSA. Additionally, in the case of SMSA SUSPICIOUS output, the user is clearly prompted to urgently contact a healthcare Provider.

e) **Reduced access and delay of care** due to increased wait times to see DPs in-office.

Potential solution: Sklip System would be used by laypersons as a stand-alone device to triage PSLCs. This could potentially improve access for persons with verified SUSPICIOUS PSLCs that require immediate in-person evaluation by a DP. FDA Clearance of the Sklip System could potentially streamline the time to treat for persons with skin malignancies who are currently delayed by the current medical system triage status quo.

The Sklip System has been reviewed by the FDA and received “Breakthrough Designation Status” with a reported overall sensitivity of 94.47% and specificity of 83.33%, compared to the highest reported accuracy by primary care providers using dermoscopy – sensitivity of 79.2% and specificity of 72.5%. The current SMSA Performance reported sensitivity for melanoma and atypical melanocytic nevi with uncertain malignant potential is 97.4% (2023).

Of note, an estimated fifty (50) percent of PSLC biopsies occur in primary care settings. The functionality of DDI based triage using Sklip System by laypersons, that is the same, or superior, to an in-person spot check visit with a primary care Provider for a layperson self-selected PSLC, could have a significant impact on streamlining and improving the safety of current patient care access. This should be evaluated in a research setting.

### 1.3 RISK/BENEFIT ASSESSMENT

In alignment with the FDA guidance mentioned above and 21 CFR 812.3(m), Sklip Inc. has determined that a clinical Study utilizing the Sklip System constitutes a **Non-Significant Risk Device Study**. From a high level, and as described in more detail following, this is because:

1. The Sklip System is not of substantial importance in diagnosing, curing, mitigating or treating disease.
2. The Sklip System does not act in a manner that the FDA guidance flags as being considered significant risk.
3. The Sklip System is not included in the list of devices that the FDA considers to be significant risk.

Therefore, the Sklip System and the Study of it can be considered a Non-Significant Risk (NSR) Device Study. Our rationale is as follows, the Sklip System is not of substantial importance in diagnosing, curing, mitigating or treating disease. Instead, the Sklip System provides a stand-alone triage assessment according to a clinical accepted protocol, where the final decision to biopsy or not and diagnosis of a PSLC is intended for confirmation by a healthcare provider.

#### 1.3.1 KNOWN POTENTIAL RISKS

There is a risk of loss of confidentiality in this Study. In addition, Participants in this Study are required to have any self-selected PSLCs to be further evaluated in-person and managed as part of normal clinical care pathways, which may result in the same increased risks associated with standards of clinical care. This includes possible increased identification of PSLCs that warrant conversion to a biopsy (as decided by a DP, not the interventional device, which may lead to increased physical biopsies and the risks associated with them. In addition, there remains the risk that a Participant in either group may miss identifying a skin lesion on their body that is malignant. However, these risks are all associated with current at-home standard of care protocol for SSEs and not increased by use of the interventional device. To provide each Participant with safety and peace-of-mind, a FBSE will be performed on each Study Participant during their in-person visit.

#### 1.3.2 KNOWN POTENTIAL BENEFITS

Participants will receive a FBSE as part of this Study as part of normal patient care with their DP after completing the Study At-home Phase. The cost of in-person patient care will not be covered by this Study as described in the Participant consent form. Scheduling, triage, biopsy, diagnosis, surgeries, treatment and other medical care for suspicious or cancerous lesions are not covered as part of this Study. However, Participants may benefit by having access to expedited time to care with a dermatology Provider (DP) which may lead to earlier detection of skin cancer, and therefore may improve patient access and outcomes. Current national wait times for in-person dermatology visits average 3 to 6 months. Participant involvement in this Study may allow the Participant to receive care much earlier (within 28 days after completion of the At-home Phase). Participants will receive free education material and training that will increase the Participant's knowledge and awareness of skin cancer and also receive the Sklip dermatoscope at no cost and can keep the device after completion of the Study.

## 2. OBJECTIVES AND ENDPOINTS

### 2.1 PRIMARY OBJECTIVES AND ENDPOINTS

Primary Objective	Endpoint	Start	End
Sklip System enables laypersons to safely triage self-selected pigmented skin lesions of concern from home with the same or better accuracy than pre-specified performance goals* for	Using all Participant PSLCs recorded in the Participant Mole Log Sheets, triage accuracy measures of the SMSA output of Participant-taken DDI will be assessed using a 2x2 table,	First day of enrollment	Up to 42 days after first day of enrollment

detection of pigmented skin lesions that require biopsy:
 
Melanoma and atypical melanocytic nevi with uncertain malignant potential (moderate, severe, and high grade atypia; those with pathology reports that include notes such as: borderline, cannot exclude melanoma, cannot exclude early evolving melanoma, unusual features, atypical spitz nevi, suspicion for melanoma, re-excision (or further removal) should be considered or is recommended in the pathologist management comment): ≥95% sensitivity, ≥30% specificity
 
Squamous cell carcinoma: ≥80% sensitivity, ≥30% specificity
 
Basal cell carcinoma: ≥80% sensitivity, ≥30% specificity
 
*Pre-specified performance goals have been reviewed with the FDA for testing the Sklip System (including SMSA) as a stand-alone device.
	
where the SMSA rating of “SUSPICIOUS” or “UNREMARKABLE” will be estimated to pre-specified accuracy metrics discussed with the FDA.
 
The Sensitivity of the SMSA using Participant-taken DDI will be estimated to pre-specified performance goals described in sections above, using 0.05 significance level and 10% margin of error.
 
Triage accuracy measures of the Sklip System (specificity, negative predictive value, positive predictive value, and accuracy) will also be calculated.
 
The Ground Truth will be the combination of the following described in the Sections above:
 
Dataset N) DDI dermoscopic diagnosis ground truth (DDI-GT) for PSLCs that were not biopsied during the In-Person Phase, and
 
Dataset O) Histologic diagnosis ground truth (H-GT) for lesions that were biopsied during the In-Person Phase
		
---	--	--	--

## 2.2 EXPLORATORY OBJECTIVES AND ENPOINTS

Exploratory Objectives	Endpoint	Start	End

1. To compare the accuracy of Sklip System triage when used by a layperson versus near-perfect Sklip System user
	
First, the Sensitivity of the SMSA using Study Coordinator-taken DDI (near-perfect technical quality) will be estimated to pre-specified performance goals described in sections above, using 0.05 significance level and 10% margin of error.
 
Similar to the Primary endpoint, the accuracy of SMSA output
	
First day of enrollment
	
Up to 42 days after first day of enrollment

	using Participant-taken DDI will be assessed using a 2x2 table, where the SMSA output of “SUSPICIOUS” or “UNREMARKABLE” will be compared to the SMSA output using Study Coordinator-taken DDI (near-perfect technical quality), simulating a laboratory-type environment where the SMSA is fed the best possible technical quality DDI.		
2. To assess whether Sklip System improves triage of pigmented skin lesions of concern < 6mm in diameter as suspicious as compared to the current medical provider virtual triage method that relies on store-and-forward non-medical-device assisted smartphone clinical images	Using only PSLs < 6 mm in diameter, the accuracy of the expert consensus triage decision using Participant-taken smartphone clinical images (SCI) will be assessed using a 2x2 table, where the expert consensus triage decision of “BIOPSY” or “MONITOR” will be compared to the intervention method, for both SMSA outputs recorded by Participants and SMSA outputs recorded by Study Coordinators for the same target PSLCs.	First day of enrollment	Up to 42 days after first day of enrollment
3. To assess whether Sklip System improves triage of thin melanomas with <0.8 mm Breslow depth as suspicious as compared to the current medical provider virtual triage method that relies on store-and-forward non-medical-device assisted smartphone clinical images	Using only Melanomas < 0.8 mm Breslow depth, the accuracy of the expert consensus triage decision using Participant-taken smartphone clinical images (SCI) will be assessed using a 2x2 table, where the expert consensus triage decision of “BIOPSY” or “MONITOR” will be compared to the intervention method, for both SMSA outputs recorded by Participants and SMSA outputs recorded by Study Coordinators for the same target PSLCs.	First day of enrollment	Up to 42 days after first day of enrollment
4. To determine the accuracy of layperson-performed SSEs at-home in the identification of all suspicious PSLs present on their body as compared to the same layperson evaluated with full body skin examination by a dermatology Provider in-person	We will calculate the following based on Participant self-skin exams (SSEs) performed during the At-home Phase:  (a) the mean and standard deviation of the number of PSLCs identified by Participants performing a SSE, and (b) the mean and standard deviation of the number of PSLCs identified by the	First day of enrollment	Up to 42 days after first day of enrollment

	dermatology Provider during the In-person Phase full body skin exam (FBSE).		
--	---	--	--

### 3. STUDY DESIGN

#### 3.1 DESCRIPTION OF THE STUDY DESIGN

*Refer to Section 11, Statistical Analysis for additional information regarding statistical methods used in this Study.*

All Participants of this single-arm prospective trial will be given up to 14 days to **review** the Sklip System instructions, **perform** a self-skin-exam (SSE) at-home, and **identify** PSLCs based on the following:

- (a) General concern (self or partner-identified, or non-dermatology Provider identified requiring a referral to a dermatology Provider)
- (b) Concern because the PSLC is different than the rest (i.e. “ugly duck sign”)

Then, Participants will be instructed to carefully follow provided instructions and **complete** the following for each target PSLC:

- 1) Mark the target PSLC with a green surgical marker (horizontal line) and the number (#) corresponding to the mole log, one (1) inch away from the target lesion
- 2) Record the target PSLC with a number (#) and anatomic location in the PMLS
- 3) Create a new photo album titled: “Moles” in their native smartphone/tablet Photo App
- 4) Take one (1) smartphone clinical image (SCI) of the target PSLC, twelve (12) inches away from the target skin lesion
- 5) Save the SCI in the album titled: “Moles” album
- 6) Review Sklip dermatoscope instructions for proper use
- 7) Take one (1) digital dermatoscopy image (DDI) of the target PSLC using the Sklip dermatoscope.
- 8) Save the DDI of the target PSLC in the “Moles” album
- 9) Upload the DDI to the SMSA (“Scan Moles with Ai”) within the Sklip App once per target PSLC, until either a Suspicious or Unremarkable result is obtained, for a maximum of three attempts. If after three attempts the user still receives an “Error” result, they will be prompted to document this in the participant mole log sheet.
- 10) Take one (1) screenshot of the SMSA output per target PSLC
- 11) Save the SMSA output screenshot in the album titled: “Moles”
- 12) Record each SMSA output (SUSPICIOUS, UNREMARKABLE, ERROR) in the PMLS once per target PSLC
- 13) Contact the Study Site to schedule an in-person FBSE within 28 days, if the Participant does not already have a scheduled visit

In summary, for each target PSLC the Participant will acquire the following:

One (1) smartphone clinical image (SCI)  
One (1) digital dermoscopy image (DDI)  
One (1) Sklip Mole Scanning Algorithm (SMSA) output recorded in the PMLS  
One (1) SMSA output screenshot

---

End of At-home Phase-----

Study Coordinators at each Study Site will conduct regular EMR chart reviews to track Participant requests to begin their In-person Phase, after the Participant has completed their the At-home Phase. These chart reviews will be conducted systematically every 7 days following Participant enrollment. Participant EMRs will be monitored for up to 28 days following conclusion of both Study Phases to account for any relevant data that may have not been collected during the Study.

---

-----Start of In-person Phase-----

---

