**With dermatology Provider present:**

The dermatology Provider (DP) will be blinded to the skin lesions that were selected by the study Participant at home. The DP will perform a FBSE as part of the normal clinical care pathway. All PSLCs identified by the DP as SUSPICIOUS will be marked with a vertical line one (1) inch away from the target PSLC using a green surgical marker. After completing the FBSE and marking all DP-selected suspicious PSLCs, the DP will verbally inform the Study Coordinator the Participant's Fitzpatrick skin phototype (1,2,3,4,5 or 6) after leaving the patient room.

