**Without dermatology Provider present,**

**with Study Coordinator present:**

The Participant will be asked to provide their Participant Mole Log Sheet (PMLS). Then, all PSLCs recorded in the PMLS will entered into REDCap Cloud by the Study Coordinator. Any Participant-selected PSLCs that match those identified earlier as SUSPICIOUS by the DP will be marked with a horizontal line one (1) inch away from the target PSLC using a green surgical marker. Therefore, PSLCs identified by both the DP and Participant will have a plus symbol. Next, the Study Coordinator will take and record (near-perfect) SCI and DDI for all PSLCs recorded in the PMLS and those PSLCs identified by the DP as SUSPICIOUS (not matching the Participant PSLCs). Then, the Study Coordinator will complete the following:

- 1) Take one (1) photo of the Participant identification sticker with a Study Site secure smartphone/tablet
- 2) Take one (1) smartphone clinical image (SCI) of each target PSLC recorded in the Participant Mole Log Sheet (PMLS)
- 3) Take one (1) digital dermoscopy image (DDI) of each target PSLC using the Sklip dermatoscope.
- 4) Save the DDI of the target PSLC in the Study Site smartphone/tablet native photo gallery
- 5) Upload the Study Coordinator-taken DDI to the SMSA ("Scan Moles with Ai") within the Sklip App
- 6) Take one (1) screenshot the SMSA output
- 7) Record each SMSA output (SUSPICIOUS, UNREMARKABLE, ERROR) in REDCap Cloud, per target PSLC
- 8) If the Participant has taken a set of SCI/DDI at home of a PSLC that is not intended (qualified because of anatomic body site) for the Sklip System, the Study Coordinator should still capture a set of control SCI/DDI and upload to REDCap Cloud. The Participant standard clinical care will not be changed.
- 9) If the Participant took a set of SCI/DDI of a PSLC at home but did not follow instructions – specifically uploading the DDI to the Sklip System - the Study Coordinator should remind the Participant to complete this task in the patient room (using the DDI from their mobile device gallery), upload to the Sklip System, and record the output on their Mole Log Sheet. If this situation occurs, the Study Coordinator should make a note in

REDCap Cloud; If the Participant is/was concerned about a PSLC but did not take a set of SCI/DDI at home, this PSLC will not be included in the study.

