## 5.3 MEASURES TO MINIMIZE BIAS

### 5.3.1 RANDOMIZATION/MASKING PROCEDURES

Blinding is considered unnecessary to reduce bias for all the observations because follow up evaluation for all Participants will follow standard clinical care pathways and is not affected by this interventional Study. The Study Site PIs and DPs will be fully blinded to all results of the At-home Phase, including the Participant Mole Log Sheet. Participants will be informed of the blinding activity prior to their FBSE to avoid DP selection-bias. Specifically, the dermatology provider will be instructed to say the following to each participant upon entering the patient room for the in-person FBSE: "Hello, my name is [name and title], the purpose of today's visit is to complete a full body skin examination as part of the at-home dermatoscopy study. To avoid bias, please hold with any questions related to your moles of concern until I have verified that I completed your full body skin examination and all other study related activities. I will be happy to address your questions or concerns at that time."

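### The protocol has participants ink a line and log number beside each selected lesion but contains no step to remove the ink before the blinded skin exam

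*Combined protocol and SAP*

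**What the plan says.** Section 3.1 gives the At-home Phase as 13 numbered steps, and the Synopsis repeats them. Step 1 is "Mark the target PSLC with a green surgical marker (horizontal line) and the number (#) corresponding to the mole log, one (1) inch away". The last step is "Contact the Study Site to schedule an in-person FBSE within 28 days, if the Participant does not already have a scheduled visit". Participants "will be given up to 14 days" for this phase. Section 8.9 asks for the exam within 28 days of completing it.

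For the exam itself, Section 3.1 states: "The dermatology Provider (DP) will be blinded to the skin lesions that were selected by the study Participant at home". Section 5.3.1 adds: "The Study Site PIs and DPs will be fully blinded to all results of the At-home Phase, including the Participant Mole Log Sheet". It also gives the provider a script asking the participant to hold back: "please hold with any questions related to your moles of concern until I have verified that I completed your full body skin examination".

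During the exam, lesions that the provider finds suspicious "will be marked with a vertical line one (1) inch away from the target PSLC using a green surgical marker". After the provider has left, participant-selected lesions that match these "will be marked with a horizontal line one (1) inch away from the target PSLC using a green surgical marker", so that a match shows as a plus.

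**The concern.** The blinding at the exam is about selection: the provider should not know which lesions the participant picked. A numbered green line an inch from a lesion discloses exactly that, on skin the provider must examine in full. The Summary of Changes gives the regulator's concern about blinding as a reason for adding the script. The script closes the spoken route; the protocol text leaves the visible one open.

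Two things depend on the exam. One is the provider's lesion count, which Exploratory endpoint 4 compares with the participant's own count. The other is the choice of lesions to biopsy, which decides the source of ground truth for each lesion. Section 8.1.2 intends that choice to be independent of what the participant found at home.

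**Working it through.** The plan gives no figure on this point, so there is none to reproduce. The check sets the relevant sections side by side.

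**1. Does any protocol step remove the ink?** The places where one could appear are:
- At-home steps 1 to 13 (Section 3.1 and Synopsis): none. After the output is logged at step 12, the participant goes straight to scheduling.
- Kit contents (Section 6.1.7): none stated. The list includes a participant instruction document whose text is not in the protocol. It names no marker, so the type of ink is not further described.
- Onboarding training (Section 6.1.8): covers the log, the follow-up visit and costs, but not the marks.
- Visit scheduling (Section 8.9) and the In-person Phase (Section 3.1): no removal, and no note of whether marks remain.
- The only removal mentioned in the imaging instructions (Section 6.1.1) is of hair.

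**2. Do the blinding safeguards reach the ink?** Section 5.3.1 covers at-home results, the log sheet and spoken questions. Section 3.1 states the requirement on selected lesions but attaches no procedure for marks on the skin. So the requirement that the ink engages most directly has no measure behind it.

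**3. How long from marking to exam?**
- Inputs: At-home Phase at most 14 days; exam at most 28 days after it; no minimum for either.
- Longest: marked at the start of a full At-home Phase and examined at the end of the window, 14 + 28 = 42 days.
- Shortest: marked on the last at-home day and examined almost at once, about 0 days. Step 13 allows for participants who already have a visit booked, so a short gap is possible.

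The interval therefore runs from about 0 to 42 days, and fading before the exam is not guaranteed by design.

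**4. What does the mark reveal?** It is drawn at step 1; the algorithm is run at step 9. The mark carries the log number and the fact of selection. It does not carry the output, and every logged lesion should have the same kind of mark whatever its result.

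**5. Where could a cue enter the analysis?**
- Exploratory endpoint 4 (Section 11.4.3) compares the participant's and provider's lesion counts by paired t-test. A cued provider count is no longer an independent comparator.
- In the primary 2x2 table (Section 11.4.2), true positives and false negatives are restricted to biopsied lesions with a histologic diagnosis. Lesions without biopsy take the dermoscopic consensus and appear only in the benign cells. A cue that changed a biopsy decision would change the source of ground truth for that lesion. By step 4, the cue is not tied to the algorithm's result, so the effect on sensitivity has no determinable direction.

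**The case against.** The strongest reply is that the workflow presumes the ink is gone. The coordinator draws a horizontal line on matched lesions after the exam, which would be redundant if the home lines were still there. Lesions are found from the log sheet and the participant's images. Participants also receive written instructions and training that may include washing the marks off. This stands as far as it goes: one can say that the protocol contains no removal step, not that participants are never told. But an implied expectation is not a procedure, and the protocol does not make it one.

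A reader might also infer more than the documents support:

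- **That the provider is in fact unblinded.** Ink persistence is not stated, and with gaps of up to about 42 days many marks may have faded. The documents show a possible route, not an occurrence or a frequency.
- **That the primary sensitivity is biased in the device's favour, or against it.** The ink shows selection only. Nothing in the plan links it to the output, so neither direction follows.
- **That leftover lines would corrupt the plus-sign record.** A residual horizontal line on a matched lesion still yields a plus, and on a participant-only lesion it remains a single horizontal line. Matching is not obviously disturbed.
- **That Section 5.3.1 is contradicted outright.** Its full-blinding sentence concerns at-home results and the log sheet, and the ink discloses no result. The requirement engaged is the one in Section 3.1. Section 5.3.1 also opens by calling blinding unnecessary, but Section 3.1 nevertheless requires the provider to be blinded to selection.

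**Conclusion.** The point holds as a minor but avoidable gap. Followed as written, the protocol places a visible sign of selection on the skin and takes no step to remove it before an exam that must be blind to selection. The main exposure is the provider count in Exploratory endpoint 4, which carries no performance goal. A secondary exposure is which selected lesions are biopsied and so receive histologic ground truth, with unknown direction.

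The size cannot be given. It depends on how long the ink lasts and on the actual distribution of days from marking to exam, and the documents state neither. The conclusion rests on the protocol text alone. If the participant instructions already call for removal, what remains is to state that step in the protocol and to record whether it worked.

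**What to change.** Insert an at-home step after step 12, in both Section 3.1 and the Synopsis: once all images are saved and the log is complete, remove all ink. Repeat it in the reminder about the visit (Section 6.1.8), and align the participant instructions with it.

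Add one yes/no REDCap field for whether any home mark was visible at the exam, completed before the coordinator draws any match line. Exploratory endpoint 4 can then be repeated without the participants for whom the answer is yes.

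The cost is one extra participant step, one data field and a routine amendment, which under Section 14.5 needs committee and IRB approval. No data are lost: the coordinator works from the log and the photographs, and a scan missed at home is run from the stored image, so no stated in-person step uses the home ink. Sample size and primary analysis are unchanged. A separate whole-body check by the coordinator before the exam is not needed; it would add a new visit step at four sites.
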